Cognitive Function – Memory function will be assessed by performance on the Hopkins Verbal Learning Test (HVLT-R), The Brief Visuospatial Memory Test (BVMT-R), and the NIH Toolbox Pattern Comparison and Flanker tests. The HVLT-T and BVMT-R have multiple versions to prevent learning tests. We will choose three versions of this test at the beginning of the trial and will administer a different version at each visit. The order will be counterbalanced to avoid any effect of test version on cognitive outcomes. The selected NIH Toolbox texts are less prone to learning effects.

Study Restrictions

Subjects must avoid over-the-counter medications for 48 hours, vigorous aerobic exercise or alcohol for 24 hours, and all food, supplements and caffeine for ≥ 12 hours before testing visit but will be allowed to consume water. There are no restrictions for Visit 1.1, unless this visit is combined with Visit 1.2, in which case the above restrictions apply.

Table 6.2. Table of Blood Tests

	Test #	Type	Volume	Visit 1.2	Visit 3.3	Visit 4.3
Screening Labs						
Comprehensive Metabolic Panel	322000	SST Serum	4 mL	X	X	X
Complete Blood Count	005009	EDTA Plasma	4 mL	X	X	X
Lipid Panel	303756	SST Serum	4 mL	X	X	X
Control Measures						
Hemoglobin A1C	001453	EDTA Plasma	4 mL	X	---	---
APOE genotype	504040	EDTA Plasma	4 mL	X	---	---
Blood Biomarkers						
Oxidative Stress/Inflammation	---	EDTA Plasma	4 mL	X	X	X

	---	SST Serum	4 mL	X	X	X				
PBMC's	---	EDTA Plasma	32 mL	X	X	X				
		Total Per Visit		60 mL (4TBL)	52 mL (3.5 TBL)	52 mL (3.5 TBL)				
				Total Volume for Study (mL)		164 mL (11 TBL)				
						Total Volume for Study (pints)				
						1/3 pint				

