Cover Page for Statistical Analysis Plan

Official Title: The effects of added sugar intake on brain blood flow and hippocampal function in midlife adults

ClinicalTrials.gov ID: NCT05211726

Protocol ID: 1760500

Date of Document: September 23, 2020

Statistical Analyses

The aims for this study will be tested using General Linear Modeling. For hypotheses H1a and H2a, a Profile Analysis (multivariate within-in subjects ANOVA) will be performed. If the omnibus test is significant, univariate within subject ANOVAs will be performed, testing the effect of diet (baseline, low sugar, and high sugar diets) on each outcome. The multivariate extension is being used to control for type-I error inflation that might occur because each aim has three primary outcomes (Aim 1: 24-hour SBP, arterial compliance, and cerebrovascular reactivity; Aim 2: HC stiffness, HC damping ratio, and delayed recall memory). All assumptions for these models will be tested, and data will be screened for outliers and influential cases. Assumptions of linearity, sphericity, and normality will be evaluated using Box-Cox, Mauchly's, and Shapiro-Wilk tests, respectively. Because some values are expressed as ratios, if the assumptions of the within subject's ANOVA cannot be satisfied by transformations suggested by the Box-Cox test then either the non-parametric Friedman test or a Generalized Linear Model will be used. Given the cross-over design, the order effect will be tested using the same model but the effect will just be time point (baseline, post diet 1, and post diet 2). If significant, the order effect will be included in the final model. A significant diet effect will be followed by pairwise comparisons using Fisher's LSD procedure. The alpha is set at 0.05 for each test. Exploratory analyses will be conducted for hypotheses H1b and H2b, using regression models testing the changes (from baseline) in each primary outcome from Aims 1a and 2a after the high sugar diet with the changes in TGs, markers of oxidative stress, and inflammation. Additionally, regression models will be used to explore whether changes in the primary outcomes from Aim 1 moderate the relation between the changes in the primary outcomes in Aim 2. This moderation will be tested by including the interaction effects of changes in outcomes from Aim 1 and 2 with the changes in TGs, markers of oxidative stress, and inflammation. During Year 2, the PI will work with the COBRE Core's lead biostatistician ([name]) to conduct an interim data analysis for an R01 proposal. The O'Brien-Fleming alpha boundary function will be used, the alpha for significance of the interim analysis is .0054 and for the final analysis is .0492.

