
Randomization, Blinding, Power & Sample Size

To enhance scientific **rigor and reproducibility**, subjects will be randomized to diet order with Group A receiving the high sugar diet first followed by the low sugar diet and Group B receiving each diet in the opposite order. Investigators responsible for data collection or analysis will be blinded to treatment condition. To address **sex as a biological variable**, we will use a block randomization scheme to ensure an even number from each sex within each treatment group and will covary for sex in our analyses. A major objective is to generate preliminary data and conduct a power analysis for an eventual R01. Power for this pilot study was determined for the profile analysis for Aims 1 and 2, testing the change across the three measurement occasions for three outcomes. This study is adequately powered (power = .80), with n=30 to detect a moderate effect ($d=.46$), for three outcomes and three timepoints with nominal alpha (.05), assuming a conservative correlation among the outcomes and repeated measures of 0.3. If the multivariate test is significant, this study is adequately powered (power = .80), with n=30 to detect a moderate effect ($d=.56$), for three timepoints with nominal alpha (.05), assuming a correlation among the repeated measures of 0.3 for follow-up univariate within subject ANOVAs. To account for drop-out or experimental error, our total recruited sample size will be 40. This effect size matches ones seen in the literature, which found a moderately large effect ($d = 0.69$ with $n=14$) in the effect of increased serum TGs within 4-5 days of a high fructose meal⁷⁵.

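### Memory-test version is counterbalanced in the design but missing from the delayed-recall model, so any difference between versions is counted as error: a small, avoidable loss of precision

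*Protocol*

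**What the plan says.** Protocol section 6.4, Cognitive Function, names two memory tests that exist in several versions, the HVLT-R and the BVMT-R. On their use it says: "We will choose three versions of this test at the beginning of the trial and will administer a different version at each visit". It continues: "The order will be counterbalanced to avoid any effect of test version on cognitive outcomes". The counterbalancing scheme is not described further.

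The SAP, Statistical Analyses, lists the outcomes concerned as "Aim 2: HC stiffness, HC damping ratio, and delayed recall memory". They go first into a multivariate profile analysis. If that is significant, "univariate within subject ANOVAs will be performed, testing the effect of diet (baseline, low sugar, and high sugar diets) on each outcome". A time-point effect is tested separately: "If significant, the order effect will be included in the final model". The section on randomization, blinding, power and sample size adds that the investigators "will covary for sex in our analyses". No model in either document contains test version, and the power calculation makes no mention of it.

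**The concern.** Counterbalancing and modelling do different jobs. Counterbalancing spreads the versions over the diets, so that a harder version does not fall mainly on one diet. It does not remove the version effect from an individual's scores. Each subject's high-sugar and low-sugar scores come from two different versions, so any gap in difficulty adds to or subtracts from that subject's difference. Without a version term the model treats this as random within-subject variation.

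What is at stake is precision on delayed recall, the only cognitive measure among the six primary outcomes. The version given at each visit can be recorded, and the design is balanced in a way that would let its effect be removed. The trial is also meant to supply a power analysis for a later grant, and an inflated within-person variance would carry into that calculation.

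**Working it through.** **Inputs from the SAP.** The power statement for the follow-up univariate test reads "with n=30 to detect a moderate effect ($d=.56$), for three timepoints with nominal alpha (.05), assuming a correlation among the repeated measures of 0.3", with stated power .80. On alpha the SAP says "The alpha is set at 0.05 for each test".

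**Step 1: reproduce the plan's figure.** For a one-way repeated-measures ANOVA with m = 3 occasions:

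- f = d/2 = .28
- noncentrality λ = f² · n · m / (1 − r) = .0784 × 30 × 3 / .7 = 7.056 / .7 = 10.08
- with 2 and 58 degrees of freedom and alpha .05, power = .797

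This agrees with the stated .80. At the final-analysis alpha of .0492 it is .795.

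**Step 2: add version differences.** The documents give no figure, so the gap D between the easiest and hardest version, in outcome SDs, is an assumption. Place the versions at −D/2, 0 and +D/2, fully balanced over diet.

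- Version omitted: the version sum of squares, n · 2 · (D/2)², falls into the 58 error degrees of freedom. The residual variance becomes .7 + 30 × 2 × (D/2)² / 58, and λ = 7.056 divided by that.
- Version modelled: the residual variance stays at .7 and 2 degrees of freedom are spent (2 and 56). Power = .796 whatever D is.

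Example for D = 0.5: 30 × 2 × .0625 / 58 = .0647, so λ = 7.056 / .7647 = 9.23 and power is .759.

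| Gap D (SD) | Added variance | Increase on .7 | Power, version omitted | Power, version modelled | Simulated type I error, version omitted |
|---|---|---|---|---|---|
| 0 | 0 | 0% | .797 | .796 | .050 |
| 0.2 | .0103 | 1.5% | .791 | .796 | .049 |
| 0.3 | .0233 | 3.3% | .783 | .796 | .046 |
| 0.5 | .0647 | 9.2% | .759 | .796 | .039 |
| 0.75 | .1455 | 20.8% | .713 | .796 | .028 |
| 1.0 | .2586 | 36.9% | .655 | .796 | .018 |

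A simulation of 20,000 trials per row, with six version orders balanced over diet, gave powers within .01 of these. To regain the planned power without a version term takes 31 completers at D = 0.3, 33 at 0.5 and 41 at 1.0.

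**Step 3: the other reading of r.** If r = .3 is the correlation between scores taken on different versions, the .7 already contains the version noise. Planned power then stays at .797, and modelling version removes the added variance from .7. For D = 0.5, λ = 7.056 / (.7 − .0647) = 11.11 and power is .836. At D = 0.2, 0.3 and 1.0 it is .803, .810 and .946.

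**Step 4: cost if the versions are equal.** With balanced versions, power moves from .797 to .796. If version orders are drawn at random without regard to diet order, version and diet are partly confounded within the sample and the term costs more. In simulation, taking .56 SD as the high-minus-low difference, power went from about .72 to .70.

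**The case against.** The strongest objection is that the size rests wholly on an assumption. Nothing in the documents says the versions differ in difficulty, and they are used as alternates of one test. Below a gap of about 0.3 SD the loss is roughly one point of power or less. The design already carries the main safeguard, and the trial is a declared pilot. All of this stands, and it is why the point is minor.

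Four stronger readings are tempting, and the documents do not support them.

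- *Version biases the diet comparison.* The protocol counterbalances version. With balance over diet the contrast is unbiased and type I error falls below .05, so omitting version does not create false positives.
- *The SAP's framework cannot hold a factor that changes by visit.* That limit applies to the multivariate profile layout. The SAP works under General Linear Modeling, and a univariate linear model with subject effects takes a version term without difficulty.
- *Version order was set without regard to diet order.* The protocol does not describe the link; it does not say there is none. Six version orders by two diet orders make 12 cells, and neither 30 nor 40 is a multiple of 12, so exact balance over all cells is not possible with six orders. That is not evidence of material imbalance.
- *Delayed recall is the only measure of brain function.* Cerebrovascular reactivity is an Aim 1 primary outcome, and the Flanker and Pattern Comparison tests are also given. Delayed recall is the only cognitive primary outcome.

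**Conclusion.** The point holds as one of efficiency. The delayed-recall model leaves out a factor that the design deliberately balances, so version differences inflate the within-subject error and the diet test is conservative. On the SAP's own univariate basis the loss is about half a point of power at a 0.2 SD gap, one point at 0.3, four at 0.5 and 14 at 1.0. These figures assume equally spaced versions, full balance over diet, 30 completers and r = .3 free of version noise. If r already includes that noise, planned power is intact and the omission forgoes a gain instead. The documents cannot show which gap applies, so they do not support a claim that delayed recall is underpowered. One of six primary outcomes is affected, and the improvement is minor but cheap.

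**What to change.** 1. For the univariate analysis of delayed recall, pre-specify a linear model with subject effects, or a mixed model with subject as random effect, and diet, visit and test version as fixed effects. Define version as that of the test from which delayed recall is scored, since both the HVLT-R and the BVMT-R have versions. Baseline is always the first visit, so visit adds only the second-versus-third contrast, and only the high-versus-low comparison can be separated from visit.
2. Assign version orders within each diet-order by sex block, for example three Latin-square orders, so that version and diet stay nearly orthogonal. With 40 subjects in four blocks (10 each) three orders do not divide evenly, so balance is close, not exact. State the scheme in the protocol.
3. For the multivariate profile test, do not subtract raw version means: if versions are unbalanced over diet, this also removes part of the diet effect. Either use version effects estimated jointly with diet, or leave that test as it is and report the version-adjusted univariate result beside it.

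Cost: 2 degrees of freedom for version, one line in the allocation list and no new data. If the versions prove equal, the version term costs under .01 of power when versions are balanced over diet, and up to about .02 when version orders are assigned at random without regard to diet order. Step 2 guards against the latter.

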6.5. Description of Research Diets

The study nutritionist will prepare two 10-day isocaloric research diets for each subject. The diets will differ in the amount of energy from added sugar sources. Added sugars include food products containing syrups and other caloric sweeteners that are added during processing or preparation of food. The majority of added sugars in the United States come from sucrose (table sugar) and products containing high-fructose corn syrup; however other sugars are also used during production or preparation of foods which are considered added sugars. Sugars found naturally in fruits, vegetables and dairy products that have not been added during processing or preparation are not considered added sugars. An example menu of each diet and the corresponding nutrient breakdown is presented in Table 6.3. The specific amount of added sugar in each research diet was selected to maximize the ability to detect changes in vascular function and brain health while also delivering a diet that is representative of current American diets. Data from the National Health and Nutrition Examination Survey (NHANES) suggest that only half of all Americans meet the current the guidelines for added sugar intake⁴, which have been set by regulatory bodies including the American Heart Association (AHA), US Department of Agriculture (USDA) and the World Health Organization (WHO) to consume less than 10% of all calories from added sugars^{10,11}. Although the average intake of added sugars (as a percentage of total calorie intake) in the United States is ~13%, those who meet current guidelines consume an average of ~5% of total energy from added sugar, whereas the average intake for those not meeting the guidelines is >20%⁴. Accordingly, the chosen amount of added sugar in the low (5% of energy) and high (25% of energy) added sugar diets are within the range of what many Americans are eating and have a high likelihood of modulating blood lipid profiles, thus enabling us to examine the effect of dietary added sugars on important physiological functions indicative of brain health.

Table 6.3. Example Menus

5% Added Sugar	25% Added Sugar
Breakfast Instant oatmeal with 2% milk and raisins Coffee with sugar and cream Snack Popcorn and peanut butter crackers Lunch Turkey sandwich with wheat bread, American cheese and mayonnaise Mini pretzels and apple Snack Tortilla chips, Baby carrots and Hummus	Breakfast Pancakes with syrup Cranberry juice cocktail Snack Coffee Cake Lunch Chicken noodle soup, saltine crackers String cheese Snack Coke-a-cola and Dry roasted almonds,

Dinner Boneless skinless chicken breast, baked potato and green beans	Oreo cookies Dinner Spaghetti and tomato sauce with ground turkey and parmesan cheese		
Nutrient Breakdown			
Carbohydrates (%)	55	Carbohydrates (%)	55
Fat (%)	30	Fat (%)	30
Protein (%)	15	Protein (%)	15
Total Calories	1,944	Total Calories	1,991
Total Carbohydrates (g/day)	271	Total Carbohydrates (g/day)	285
Total Sugar (g/day)	77	Total Sugar (g/day)	157
Added Sugar (g/day)	25	Added Sugar (g/day)	131
Added Sugar (% Kcal)	5	Added Sugar (% Kcal)	25
Fiber (g/day)	26	Fiber (g/day)	12

Diet Adherence

During the strictly controlled diet periods, all meals and snacks will be provided to the subjects. Food for the 10-days will be packed in a cooler and picked up by the subjects at Visits 3.1 and 4.1. All food preparation will be overseen by our registered dietitian and prepared in the metabolic kitchen in the Tower at STAR. Energy needs will be calculated at baseline using the Mifflin-St. Jeor equation¹¹ and will be corrected for habitual physical activity in order to ensure weight stability throughout the study. Subjects will be asked to consume only the provided food. No other food should be eaten during either of the 10-day diet periods. Subjects will be asked to report extra food items using the "Extra Food Log" form as well as bring back any uneaten food to be weighed. If it is determined that a subject is eating "outside foods" (>50 kcal on 2 or more days), they will be terminated from the study. The total calories provided are designed to keep the subjects weight stable during this period (this is referred to as "isocaloric"). We will also provide them with water (bottled) to drink during each diet. Subjects will report to the lab on the 10th day of each diet to undergo all post-intervention testing (Visits 3.2, 3.3, 4.2, & 4.3).

Washout Period

Subjects will complete a 2-week washout period in between each diet to ensure enough time for lipid markers and physiological functions to return to baseline values between diets. Previous dietary intervention crossover studies over a 3-6 week period *without* a washout period have **not** reported carryover effects on measures of large elastic artery stiffness, vascular function or cognitive performance^{13,14}. Accordingly, we expect the proposed measures of physiological function to return to baseline quickly and the proposed 2-week washout period represents a conservative approach.

7. STUDY POPULATION AND RECRUITMENT

Study Population – The target enrollment for this study is 200 healthy adult men and women between 50-64 years of age, with a target completion of 40 participants. This age group has been defined by NIH as being at high risk of accumulating cardiometabolic risk factors that preclude chronic age-related diseases¹⁵⁻¹⁷. To avoid any influence of baseline diet (e.g., chronic consumption of a high-sugar diet prior to enrollment), will only enroll those with a habitual intake of added sugar that is reflective of the average American intake (~13% of total calories) based on the National Health and Nutrition Examination Survey (NHANES)¹⁸. This will increase the likelihood of observing changes in our primary outcome variables in response to the proposed research diets which are designed to deviate from baseline proportion of added sugars by about 10% of calories in each direction. Importantly, even if

subjects are close to the upper or lower cutoff, we are still likely to observe changes in primary outcomes when placed on the opposite arm of the crossover. Because this is a pilot study, we will analyze the data after the first 5-10 participants have completed the trial and ensure that we are seeing an effect of the diets on the primary outcome variables. If we do not see an effect, we will amend the protocol to increase the duration and/or modify the composition of the diets.

To be eligible to participate, volunteers must meet the following specific enrollment criteria:

Inclusion Criteria:

- ability to provide informed consent;
- men and postmenopausal women aged 50-64 years;
- habitual intake of added sugars ≤15% of total calories¹⁸;
- systolic BP < 130 mmHg; diastolic BP < 90 mmHg¹⁹;
- body mass index (BMI) <30 kg/m² and % body fat < 25% for men and < 33% for women
- fasting triglycerides < 200 mg/dl (< 2.3 mmol/L)²⁰;
- LDL cholesterol <160 mg/dl (4.14 mmol/L)²¹
- fasting plasma glucose <126 mg/dl (<7.0 mmol/L) and hemoglobin A1C < 6.5% at screening²²;
- weight stable in the prior 6 months (≤ 2 kg weight change);
- blood chemistries indicative of normal liver enzymes and renal function (estimated glomerular filtration rate using the MDRD prediction equation must be >60 ml/min/1.73 m²)

Exclusion Criteria:

- current use of medications or supplements known to lower blood triglycerides or cholesterol (e.g., fibrates, statins, high dose niacin, high dose omega-3 supplement);
- chronic clinical diseases (e.g., coronary artery/peripheral artery/cerebrovascular diseases, heart failure, diabetes, chronic kidney disease requiring dialysis, neurological or autoimmune conditions affecting cognition (e.g. Alzheimer's disease or other form of dementia, Parkinson's disease, epilepsy, multiple sclerosis, large vessel infarct);
- major psychiatric disorder (e.g. schizophrenia, bipolar disorder);
- major depressive disorder (PHQ-9 ≥ 10);
- current or past (i.e., last 3 months) use of anti-hypertensive or other cardiovascular-acting medications known to influence vascular function and/or arterial stiffness^{23,24};
- current medication use likely to affect CNS functions (e.g. long active benzodiazepines);
- concussion within last 2 years and ≥ 3 lifetime concussions²⁵;
- heavy alcohol consumption (defined by the CDC and USDA as ≥8 drinks/week for women and ≥15 drinks/week for men)²⁶.
- claustrophobia, metal implants, pacemaker or other factors affecting feasibility and/or safety of MRI scanning;
- recent major change in health status within previous 6 months (i.e., surgery, significant infection or illness);
- current smoking within the past 3 months.
- High degree of physical activity as defined by ≥ 25 leisure MET-hours/week, within the past 3 months.

Recruitment

Subjects will be recruited from Newark, DE and the surrounding area. Recruitment methods may include posted flyers, digital advertisements (e.g., Facebook), direct mailings to age-specific regional mailing lists, UD alumni and employee mailing lists, UD press releases, information sharing with a

variety of minority organizations associated with UD and the Newark community, participation in health fairs, and emails sent to past participants interested in being recontacted about new research studies.

Primary Exit Criteria

- Completion of the study;
- Failure to eat the diet during the dietary trial;
- Eating foods other than those prepared for the subject during the dietary intervention (>50 kcal/day on 2 or more days);
- Not showing up to the agreed upon study visit two times or chronically canceling within 2 hours of the agreed upon visit (two times);
- Failure to complete MRI scanning (e.g., due to claustrophobia);
- Donating blood or a large volume of blood drawn within 6 weeks of study participation or during the study (subjects should not donate blood in 6 weeks following study participation).

Subjects will also have the option of withdrawing from the study at any time for any reason. The number of subjects exiting the study and the reasons for exit will be carefully documented. Subjects who withdraw from the study will be replaced in order to achieve the sample size required for appropriate statistical power.

